## **10.2 ADVERSE EVENT MANAGEMENT:**

The following adverse event management guidelines are intended to ensure the safety of each subject while on the study. Adverse events and adverse device effects will be attributed to study procedure and graded by severity according to the following tables:

### **10.2.1 Grading of adverse events and adverse device effects**

| Category | Description   |
|----------|---|
| Mild     | Awareness of symptom. Not expected to have a clinically significant effect on the subject's condition. Not surpassing the expected standard medical intervention. |
| Moderate | Condition creates a level of discomfort that interferes with the subject's usual activity or affects clinical status. May require medical intervention.           |
| Severe   | Incapacitating and significantly affects the subject's clinical status. Likely requires medical intervention and prolonged hospitalization.                       |

### **10.2.2 Attribution of adverse events to the research protocol**

The relatedness of adverse events will be classified as:

| Classification | Description  |
|----------------|--|
| Definite       | The event is clearly related to the research protocol.   |
| Probable       | The event is likely related to the research protocol. The event has a reasonable temporal relationship to the research device or research procedure and alternative causes, such as underlying disease, concomitant medications, or concomitant treatment-can be excluded.   |
| Possible       | The event may be related to the research protocol. The event has a reasonable temporal relationship to the research device or research procedure, and attribution of the event to the device or procedure cannot be excluded. However, alternative causes—such as underlying disease, concomitant medications, or concomitant treatments—are presumably responsible. |
| Unlikely       | It is doubtful the event is related to the research protocol. The event can reasonably be explained by other factors, including underlying disease, concomitant medications, or concomitant treatments.  |
| Unrelated      | The event is clearly not related to the research protocol. There either is no temporal association with the research device or procedure, or the event is readily explained by other factors, including underlying disease, concomitant medications, or concomitant treatments.  |

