## 9.2 STUDY ANALYSIS

Analyses will be performed using principles both of (1) intention-to-treat, defined as attempting or initiating Transcatheter Mitral Cerclage Annuloplasty, and (2) as-treated, defined as completing Transcatheter Mitral Cerclage Annuloplasty. We expect these to be the same.

Clinical events are classified by the site Principal Investigator and confirmed by the NIH Principal Investigator. The results of the study will be released within 12 months of study completion.

The study will be analyzed using descriptive statistics, including a case-by-case narrative summary of major adverse events. Representative descriptive statistics include typical demographic features (age, sex, comorbidity), symptoms (NYHA heart failure classification), ventricular geometry and function (volumes, ejection fraction), hemodynamics (chamber pressures), procedure characteristics (procedure time, contrast exposure), etc.

We will attempt to stratify subjects by various phenotypes (HFrEF vs HFpEF, MR severity, dimensions) and associate these with measurements (cerclage geometric shortening), and outcomes (symptom status, functional status, change in chamber volumes and regurgitation, adverse events), as allowed by the small sample size.

Afterwards, we will survey for parameters associated with an increased risk of major adverse events.

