#### **10.0 ADVERSE EVENT REPORTING**

##### **10.1 DEFINITIONS**

*Adverse events:* Any untoward medical occurrence in a human subject, including any abnormal sign (e.g., abnormal physical exam or laboratory finding), symptom, or disease, temporally associated with the subject's participation in the research, whether or not considered related to the subject's participation in the research.

This will include:

- Expected events related to the subject's disease process during active enrollment in the research protocol and do not directly result from use of the investigational device or study.
- Procedural events directly related to the cardiac catheterization procedure and recovery from the procedure and do not directly result from use of the investigational device.

*Serious Adverse Event (SAE):* A serious adverse event that results in any of the following and NOT directly related to the device. This includes any event that

- Results in death
- Is life-threatening (places the subject at immediate risk of death from the event as it occurs);
- results in in-patient hospitalization or prolongation of existing hospitalization;
- results in a persistent or significant incapacity;
- results in a congenital anomaly/birth defect (not relevant to this study); or
- based upon appropriate medical judgment, may jeopardize the subject's health and may require medical or surgical intervention to prevent one of the other outcomes listed in this definition.

*Adverse Device Effect (ADE):* Any untoward or unintended response to a medical device. This definition includes any event resulting from insufficiencies or inadequacies in the instructions for use or the deployment of the device or any event that is a result of user error.

During this clinical investigation an event should be considered related to the device when it is the result of:

- Transcatheter Mitral Cerclage Annuloplasty procedure
- Transcatheter Mitral Cerclage Annuloplasty device

An event will be considered NOT related to the Transcatheter Mitral Cerclage Annuloplasty procedure when it is the result of a pre-existing medical condition.

*Anticipated Adverse Device Effects (AADEs):* An AADE is an adverse event with a reasonable possibility that the device or procedure caused or contributed to the event. The following AADEs are considered anticipated based on judgement and clinical experience:

- Death

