***Serious Adverse Device Effect (SADE):*** An adverse effect that may have been or is attributed to the use of the device and produce an injury or illness that is life-threatening, results in permanent impairment or damage to the body, or requires medical or surgical intervention to prevent permanent harm to the body.

***Unanticipated Adverse Device Effect (UADE):*** Any serious adverse effect on health or safety or any life-threatening problem or death caused by, or associated with, a device, if that effect, problem, or death was not previously identified in nature, severity, or degree of incidence in the investigational plan or application (including a supplementary plan or application), or any other unanticipated serious problem associated with a device that relates to the rights, safety, or welfare of subjects (21 CFR 812.3(s)).

***Unanticipated Problem (Up):*** An unanticipated problem is any incident, experience, or outcome that meets ALL of the following criteria:

- Unexpected in terms of nature, severity, or frequency in relation to:
  - a. the research risks that are described in the IRB-approved research protocol and informed consent document, Investigator's Brochure or other study documents, and
  - b. the characteristics of the subject population being studied, and
- Related or possibly related to participation in the research, and
- Suggests that the research places subjects or others at a greater risk of harm (including physical, psychological, economic, or social harm) related to the research than was previously known or expected.

***Unanticipated Problem that is not an Adverse Event:*** An unanticipated problem that does not fit the definition of an adverse event, but which may, in the opinion of the NIH and site Principal Investigators,

involves risk to the subject, affect others in the research study, or significantly impact the integrity of research data. For example, report occurrences of breaches of confidentiality, or accidental destruction of study records.

*Protocol Deviation:* A protocol deviation is any change, divergence, or departure from IRB-approved research protocol.

*Major Deviations* - Deviations from the IRB approved protocol that have, or may have the potential to, negatively impact, the rights, welfare or safety of the subject, or to substantially negatively impact the scientific integrity or validity of the study.

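### The five relatedness grades leave a gap and overlap, and Section 10.1 has no rule for mixed causes, so the same serious event can be filed as SAE or SADE

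*Combined protocol and SAP*

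**What the plan says.** Section 10.2.2 grades relatedness as Definite, Probable, Possible, Unlikely or Unrelated. Probable needs a reasonable temporal link, and that "alternative causes, such as underlying disease, concomitant medications, or concomitant treatment-can be excluded". Possible needs the same link, and that "attribution of the event to the device or procedure cannot be excluded". It then adds: "However, alternative causes—such as underlying disease, concomitant medications, or concomitant treatments—are presumably responsible". Unlikely covers events of doubtful relation that other factors could reasonably account for. Unrelated covers events with no temporal link, or with a ready explanation elsewhere.

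Section 10.1 sets further tests:

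- An event is device-related when it results from the procedure or the device.
- On the other side: "An event will be considered NOT related to the Transcatheter Mitral Cerclage Annuloplasty procedure when it is the result of a pre-existing medical condition".
- For anticipated effects: "An AADE is an adverse event with a reasonable possibility that the device or procedure caused or contributed to the event".
- A SADE is "An adverse effect that may have been or is attributed to the use of the device", with a seriousness condition.
- An SAE is a serious event that is not directly device-related.

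No sentence says which of the five grades count as device-related. On who decides, Section 9.2 states: "Clinical events are classified by the site Principal Investigator and confirmed by the NIH Principal Investigator". Section 9.6 gives the Clinical Events Adjudication Committee (CEAC) relatedness review of first-year deaths, technical success and procedural success only.

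**The concern.** A relatedness scale should give every event one grade, and that grade should decide whether the event is reported as a device effect. Here neither step is secure. All subjects have symptomatic heart failure, and Section 10.1 lists heart failure, cardiogenic shock and ventricular arrhythmia among the anticipated device effects. For such an event, underlying disease can be hard to rule out.

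The study has no control arm and its objective is feasibility and safety. Event-by-event attribution is therefore a principal means of separating device harm from disease. If the wording supports two filings of one event, counts of serious device effects depend partly on which sentence a site applied.

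**Working it through.** No stated figure is involved, so the check sets the definitions side by side.

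**Step 1: the grades.** Take an event with a reasonable temporal link, not clearly due to the device, for which the device or procedure cannot be ruled out. Vary only the standing of the alternative cause.

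| Alternative cause | Grades whose wording fits |
|---|---|
| (a) Ruled out | Probable |
| (b) Plausible, but device favoured | Neither Probable nor Possible; only the second sentence of Unlikely, against its first |
| (c) As plausible as the device | As (b) |
| (d) Presumed responsible | Possible, and the second sentence of Unlikely |
| (e) Readily explains the event | Possible, Unlikely and Unrelated |

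Rows (b) and (c) are the gap. Rows (d) and (e) are the overlap. In row (b) the closest literal match places an event that favours the device below Possible.

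**Step 2: the Section 10.1 tests.** Take serious worsening of heart failure on day 20 (an assumed example), with device and disease both plausible.

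- SADE wording: the device may have been the cause, so the event is a SADE.
- Anticipated-effect wording: the device may have contributed, so it is an anticipated device effect.
- SAE wording: it is not shown to be directly device-related, so it is an SAE.
- Pre-existing-condition sentence: if the site regards it as the result of prior heart failure, it is not procedure-related, and again an SAE.

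Each filing has support in the text, and no rule ranks the tests when causes are mixed.

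**Step 3: what changes with the label.** In the site table of Section 10.2.4, a SADE is due to the sponsor within 3 working days and an SAE within 5. The difference is 5 − 3 = 2 working days.

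**Step 4: scale.** Section 9.1 plans 30 attempted procedures. One subject reclassified moves a per-subject rate by 1/30 = 3.3 percentage points. The documents do not say how many subjects would be affected, so the total cannot be derived.

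**Step 5: what does not depend on the label.** The stopping rule in Section 9.9 counts all deaths within 30 days. First-year deaths and the two success endpoints have CEAC relatedness review, although the plan gives the CEAC no separate relatedness criteria. Section 9.6 lists no other serious events, and nothing after the first year, for that review, while Section 10.2.3 continues SAE and SADE reporting at annual visits.

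**The case against.** The strongest reply is that the device definitions lean towards inclusion. The SADE wording takes in effects that only may be due to the device, the anticipated-effect wording takes in contribution, and the Possible grade itself opens by allowing a relation. On that reading mixed-cause events are captured. This stands to the extent that under-counting is possible, not inevitable.

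Three stronger readings are tempting and should not be drawn.

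- A reader might infer a built-in default towards not related. None is stated. The pre-existing-condition sentence applies when an event is the result of that condition; Possible only presumes another cause and keeps the device open.
- A reader might infer that the day-20 example alters procedural success. Section 9.4.1 restricts that item to specified bleeding, vascular or cardiac complications that need unplanned reintervention or surgery, and the CEAC reviews it. Heart failure or arrhythmia without reintervention would not fail it under either label.
- A reader might infer that UADE status turns on the label. Both kinds of event are listed as anticipated, so a UADE would need unexpected severity or incidence.

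Oversight is also substantial: case narratives of major adverse events, 30-day data to FDA for each cohort of 5, DSMB review every six months, and full source-data verification. Filing as an SAE does not clearly weaken it: the NIH Principal Investigator's table sends SAEs to the Clinical Director within 14 days and has no separate SADE row. Nor is any device-related rate tested, since Section 9.1 sets no acceptance criterion and the analysis is descriptive.

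Finally, counting every Possible event as device harm is debatable in an uncontrolled heart failure cohort, because it could over-count. That stands and shapes the fix. None of these points supplies a grade for rows (b) and (c) or a rule for mixed causes.

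**Conclusion.** The defect is real and minor. The grades are neither exhaustive nor mutually exclusive, and Section 10.1 applies inconsistent tests without a mixed-cause rule. This is a fault in stated rules, since sites that follow them exactly can disagree. The consequence is inconsistent SAE or SADE filing, a 2-working-day difference in the sponsor deadline, and possible under-counting of serious device effects at 3.3 percentage points per subject affected.

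A reader might go further and expect a sizeable under-count. The documents give no frequency of mixed-cause events, so neither the size nor the direction of the net error can be established. The conclusion assumes a literal reading and that no separate instruction settles the matter; Sections 9.6 and 13.5 contain none.

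**What to change.** 1. In Section 10.2.2, reword Probable as *more likely due to the device or procedure than to alternative causes*, and Possible as *device or procedure cannot be excluded and alternative causes are also plausible*. Limit Unlikely and Unrelated to events where another cause is clearly favoured, and state what separates those two, for example whether the device or procedure can be ruled out.
2. In Section 10.1, reconcile the tests so that an event to which the device or procedure may have contributed is not classed as unrelated merely because a pre-existing condition also contributed.
3. Report serious device-related counts both ways: Definite and Probable only, and with Possible included. Apply the same wording to events already graded.

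This shows the reader how far the counts depend on attribution without settling whether Possible events are device harm. It leaves the definition of procedural success unchanged.

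The cost is a few sentences, a case report form note, and brief re-grading of earlier events; Section 3.0 shows that at least ten subjects had been treated by Amendment F. Device-related counts may look slightly less favourable.

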### **10.2.3 Adverse Event Reporting**

Adverse event recording will start on Day (0) of the Transcatheter Mitral Cerclage Annuloplasty procedure and will continue through the 12 month Follow Up. Assessment, recording and reporting of serious adverse events (SAE) and serious adverse device effects (SADE) will continue at annual visits thereafter.

New events or conditions present at baseline that increase in severity will be recorded and evaluated and reported on the case report form. Once the subject has completed the 30 day follow up, only serious adverse events (SAE), serious adverse device effects (SADE), unanticipated device effects (UADE) and unanticipated problems (UP) will be reported to the Sponsor . It is the responsibility of the site Principal Investigator to report adverse events and adverse device effects to the IRB of record, to the study sponsor, and to other regulatory bodies according to their reporting requirements. Monitoring visits will be conducted by the Sponsor to review source documentation, and accuracy and completion of the adverse event case report forms.

Section 5.4.1 enumerates blood tests that are monitored for adverse events. No other blood test are reported as adverse events.

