## 9.4 SECONDARY ENDPOINTS

### 9.4.1 Procedural success

The secondary endpoint is **Procedural success**. This endpoint is measured at 30 days. All of the following must be present

- Technical success
- No cerclage device-related Serious Adverse Device Effects, defined as VARC-2 life-threatening bleeding, major vascular or cardiac complications related to the cerclage requiring unplanned reintervention or surgery

Such reinterventions are directly related to the valve. Pacemaker implantation, for example, is consistent with procedural success.

The secondary endpoint is classified by the NHLBI Principal Investigator and reviewed for possible reclassification by the Clinical Events Adjudication Committee.

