#### **9.10 OFF STUDY CRITERIA**

- Completion of the 5-year follow-up
- The subject voluntarily withdraws
- The cerclage procedure fails and no implant is left behind, after the first 30 day assessment
- Significant subject non-compliance with follow-up visits, despite repeated site Principal Investigator effort to assure compliance including telephone encouragement and registered letter reminders if necessary.
- Death

Confirmation of survival will be sought from all subjects, even after they voluntarily withdraw, by contacting their physicians, the social security death index, and the subjects themselves.

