#### **10.2.5 Interim reporting to FDA CDRH for Early Feasibility Study**

For each sequential cohort of 5 subjects, we will summarize and transmit the 30-day data to FDA CDRH.

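### A compliant 30-day visit can fall on day 16 and releases failed-implant subjects from the study, so their non-fatal events may go uncollected for up to 14 days before day 30

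*Combined protocol and SAP*

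**What the plan says.** All references are to the combined protocol and SAP.

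- **Visit window.** Both parts of the schedule in section 5.4 give the 30-day follow-up a tolerance of 14 days either way.
- **Reporting to the sponsor.** Section 10.2.3: "Once the subject has completed the 30 day follow up, only serious adverse events (SAE), serious adverse device effects (SADE" and the unanticipated device effects and problems are then reported. The trigger is completion of the visit.
- **Recording.** The same section says "Adverse event recording will start on Day (0) of the Transcatheter Mitral Cerclage Annuloplasty procedure and will continue through the 12 month Follow Up", and also "New events or conditions present at baseline that increase in severity will be recorded and evaluated and reported on the case report form". For the years after that, "serious adverse events (SAE) and serious adverse device effects (SADE) will continue at annual visits thereafter".
- **Leaving the study.** One off-study criterion in section 9.10 is "The cerclage procedure fails and no implant is left behind, after the first 30 day assessment". The section adds: "Confirmation of survival will be sought from all subjects, even after they voluntarily withdraw".
- **Uses of the 30-day horizon.** For procedural success, section 9.4.1 says "This endpoint is measured at 30 days". Section 10.2.5 says "For each sequential cohort of 5 subjects, we will summarize and transmit the 30-day data to FDA CDRH". Section 9.9 monitors deaths within 30 days.
- **Analysis set.** Section 9.2 defines intention-to-treat by an attempted or initiated procedure, so a failed implant still counts.

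Neither section 9.10 nor section 10.2.3 says that its cut-off cannot apply before day 30.

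**The concern.** A 30-day safety summary implies that each subject was observed for 30 days. Here two cut-offs depend on a visit that may take place on day 16, so a site can follow the plan exactly and still fall short of the horizon.

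The weak point is the subject whose procedure failed and who leaves without an implant. That subject may have had jugular and arterial access and instrumentation of the coronary veins or septum (section 5.3). Several anticipated effects in section 10.1, such as perforation with effusion, access bleeding and infection, do not need a retained device. Appendix A answers several failure modes by aborting the procedure and expecting no permanent harm. Observation of these subjects is what would test that expectation, and the off-study rule can end it early. An event that is not collected can only lower the count.

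Safety is a stated objective (section 1.0) and only 30 attempted procedures are planned. The FDA summaries cover five subjects each, so one subject is 1/5 = 20% of a cohort.

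**Working it through.** The plan states no figure for this point, so the check is date arithmetic followed by a comparison of the rules.

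**Inputs.** Nominal day 30 and tolerance 14 days (section 5.4); Day 0 is the procedure.

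**Dates.**
- Earliest compliant visit: 30 − 14 = day 16.
- Latest compliant visit: 30 + 14 = day 44.
- Largest shortfall against day 30: 30 − 16 = 14 days (days 17 to 30), and 14/30 = 46.7% of the period.
- A visit on day 30 or later leaves no shortfall.

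**What ends after a day-16 visit.**

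| | Implanted subject | Failed procedure, no implant |
|---|---|---|
| Non-serious events, separate report to sponsor | Ends (10.2.3) | Ends (10.2.3) |
| Non-serious events, case report form | Continues to 12 months (10.2.3) | No provision once off study (9.10) |
| Non-fatal serious events | Still reportable (10.2.3) | No provision once off study (9.10) |
| Deaths | Still reportable (10.2.4) | Survival check, undated (9.10) |

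**Procedural success.** It requires technical success and no qualifying serious device effect (section 9.4.1). In an implanted subject such effects stay reportable after the visit. A subject left without an implant has already failed technical success, which requires successful deployment (section 9.3), so a missed later event cannot change the classification.

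**Mortality rule.** Thirty-day deaths remain countable if the survival check is done. To show what depends on that condition, I first reproduced the plan's own figure. With the section 9.9 boundary (2 deaths for n = 2–5, 3 for 6–12, 4 for 13–20, 5 for 21–28, 6 for 29–30) and N = 30, the exact stopping probability at a true mortality of 20% is 75.9%, against 76% stated.

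Now suppose, beyond anything in the documents, that a share f of procedures fails, all of these subjects are seen on day 16, deaths are spread evenly over 30 days, and no check is made afterwards. The observable rate is then 0.20 × (1 − f × 14/30):
- f = 5%: 0.195, stopping probability 74.0%.
- f = 30%: 0.172, stopping probability 63.5%.

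This illustrates a survival check that is not done. It is not an estimate for this trial.

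**After the fix.** With the cut-off at max(day 30, visit day), the shortfall is 0 days for every compliant visit.

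**The case against.** A reader might infer that all 30-day safety data can stop two weeks short. The documents do not support that. For implanted subjects, events are recorded to 12 months, case report forms are due within 7 days of an event (section 13.5), and full source-data verification is planned (section 14.2.4). A non-serious event on day 20 in such a subject is still recorded and visible to the sponsor. What ends is the separate report.

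A reader might also infer that the secondary endpoint or the mortality rule is biased. Neither follows. Procedural success cannot change, for the reason shown in the working. Deaths are covered by the survival check and by the requirement to report a death within 3 working days (section 10.2.4).

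Three further points have weight. Section 9.2 expects the attempted and completed sets to be the same, so the sponsor anticipates few or no failed implants. The off-study wording could be read as an assessment covering the first 30 days. And section 10.2.5 does not say that the FDA data are cut at the visit date.

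What stands against these is narrow. A rule for failed implants exists, so the case is foreseen. Its wording does not exclude day 16, and no other section provides for collecting non-fatal events once such a subject is off study. Section 10.2.3 also does not say whether the case report form or the sponsor reports feed the 30-day summary. For an implanted subject seen early, the next scheduled clinic visit is at 6 months. The CT at 30–90 days is imaging only and may be postponed or omitted for renal function.

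**Conclusion.** The point holds in a limited form. For subjects whose procedure failed and who have no implant, compliant conduct can leave non-fatal events, serious ones included, uncollected for up to 14 days before day 30. For implanted subjects only the separate reporting of non-serious events to the sponsor is affected.

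The 14 days (46.7% of the period) is a worst case for a subject seen on day 16, not an average. The documents give neither the share of early visits nor the failure rate, so the number affected is unknown and may be small. The conclusion assumes that the ±14-day window applies to the assessment named in section 9.10, and that going off study ends event collection other than survival. The finding for mortality assumes that the survival check is carried out and establishes status at day 30.

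This does not undermine the primary or secondary endpoint. It is a wording gap in safety follow-up that is worth closing because the study is small and closing it costs almost nothing.

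**What to change.** Keep the ±14-day window for the tests; narrowing it is not needed. Then:

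1. In section 9.10, let a subject with a failed procedure and no implant leave the study at the later of day 30 and completion of the 30-day assessment.
2. In section 10.2.3, narrow sponsor reporting at that same later date.
3. For any subject seen before day 30, add a phone or record-review contact on or after day 30 covering vital status, adverse events and reintervention. Section 5.4 already accepts this kind of contact for the long-term assessments.
4. In section 10.2.5, summarise a cohort's 30-day data only after that contact, and state which records feed the summary.

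The cost is a few lines of wording and at most one extra phone call per subject seen early. Subjects seen on or after day 30 need nothing more.
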